The 3-day food diary will be blinded and analyzed by a registered dietitian using NutritionistPro Software (Stafford, TX).

Statistics

Data analysis will be based on the intention-to-treat principle where all patients will be analyzed as part of their randomization group regardless of subsequent events. We will also perform a secondary analysis on patients that complete at least 8 weeks of treatment. The goal of this aim is to understand the mechanisms by which vitamin D affects vascular function on patients with diabetes and hypertension assessed by blood pressure, flow mediated dilatation and systemic inflammatory markers. Analyses are based on the fact that the primary (SBP and DBP) and secondary (FMD) outcomes are continuous and are measured at multiple time points. Between group comparisons of baseline characteristics will be performed using unpaired t-tests (for continuous measures) or chi-square tests (for categorical measures). To account for the possibility that there will be missing data in some patients, hypotheses regarding the equality of changes over time in the two groups will employ mixed model repeated measures analyses of variance with the primary focus on the significance of the interaction between group and time point. Statistical contrasts will test specific hypotheses regarding between-group differences in changes between select time points. Subsequent analyses of covariance will be performed to evaluate the impact of potential confounding variables that differed between groups at baseline.

Confounds that could influence the response include BMI, body weight, smoking status, season, sun exposure, and dietary intake of sodium, potassium, calcium, and vitamin D. Multiple regression will also be used to determine the influence of changes in these confounds on the outcomes. For all analyses, careful attention will be given to whether the data satisfy the distributional and model-specific assumptions of the procedures used.

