Appropriate data transformations or non parametric methods will be used as appropriate. We proposed to recruit 120 patients for this study. Assuming a 20% dropout rate, 90% power calculation was performed to determine the magnitude of between-group differences that can be detected with the sample size of 48 patients per group. The type-I error rate was set at $\alpha=0.05$ with a two-tailed unpaired t-test and conservative projected standard deviations (SDs) based on the investigator's pilot data and Pfeifer, et al.⁵⁷ The planned study with 48 patients completing the intervention affords excellent power to detect meaningful differences for the primary outcomes; with minimum detectable differences ranging between 10 to 15 mm Hg and 5 to 10 mm Hg for SBP and DBP, respectively. Although the study is not powered for the secondary endpoint of FMD, the study yields power of more than 0.90 to detect a minimum difference of 2% (assuming an SD=2.5).

Data and Safety Monitoring Plan

We will minimize the patient's risks by careful screening and frequent physician visits (every 2 weeks for the first 6 weeks) to the clinic, where the patient will be educated about the signs and symptoms of hypertension, hyper- and hypocalcemia and kidney stones. We will also monitor the patients' BP, serum calcium, and urinary calcium levels during these visits. To prevent vitamin D toxicity, we will assess a random sample of vitamin D pill content.

All data will be used for research purposes. The risk of loss of confidentiality will be minimized by adherence to HIPAA guidelines established by Washington University. Data analysis will be based on the intention-to-treat principle where all patients will be analyzed as part of their randomization group regardless of subsequent events. We will also perform a secondary analysis on patients that complete at least 8 weeks of treatment. ClinPortal will be used to collect, store and disseminate project-specific clinical and translational research data

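### The primary mixed model uses baseline BP only as a repeated outcome, not as a covariate: valid, but less precise than it could be; the supportive ANCOVAs pick covariates by observed imbalance

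*Combined protocol and SAP*

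**What the plan says.** The Statistics section names SBP and DBP as primary and asks whether they change equally in the two arms. The tool is "mixed model repeated measures analyses of variance with the primary focus on the significance of the interaction between group and time point". It adds that "Statistical contrasts will test specific hypotheses regarding between-group differences in changes between select time points", without naming the time points. No covariate is listed for this model, and nothing is said about a common baseline mean.

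Covariates come later. "Between group comparisons of baseline characteristics will be performed using unpaired t-tests" (chi-square tests for categorical measures), and subsequent analyses of covariance are then run "to evaluate the impact of potential confounding variables that differed between groups at baseline". No threshold for a difference is given. The text goes on: "Confounds that could influence the response include BMI, body weight, smoking status, season, sun exposure, and dietary intake of sodium", then potassium, calcium and vitamin D. That makes nine variables, and baseline BP is not among them. A further multiple regression uses changes in these variables, so it does not adjust for baseline either.

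The sample-size paragraph of the same section uses a two-sided unpaired t-test at 0.05 with 48 per group: "Assuming a 20% dropout rate, 90% power calculation was performed". It reports "minimum detectable differences ranging between 10 to 15 mm Hg and 5 to 10 mm Hg for SBP and DBP, respectively". No BP SD is stated, nor whether the SDs are of raw values or of changes.

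**The concern.** With baseline as a time point and the baseline means of the two arms left free, the group-by-time comparison is a comparison of change scores. This takes account of baseline with a slope fixed at 1. Unless r is close to 1, the best slope is below 1, and fixing it at 1 adds noise to the treatment estimate. The baseline measurement is already collected, so the lost precision could be recovered at no cost to patients.

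The supportive ANCOVAs raise a separate question. A chance difference between arms says little about whether a variable predicts BP. Under the imbalance rule, a strong predictor that happens to be balanced is left out, a weak one that happens to differ is put in, and the adjusted model is not known until the data are seen.

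**Working it through.** **Inputs from the plan.** 120 recruited; 20% dropout; 48 per group; two-sided 0.05; 90% power; detectable differences of 10–15 mmHg (SBP) and 5–10 mmHg (DBP); ABPM at baseline, 8 and 16 weeks; qualifying ABPM of 120–160/80–100 mmHg (Protocol section).

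**Assumptions, not in the plan.** The primary BP is the three-visit ABPM, and the qualifying ABPM serves as baseline. The correlation r is equal between all visits, at 0.5 to 0.7. For the range restriction, baseline BP before restriction is normal with mean 138/85.

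**1. The plan's own figures.**
- 120 × 0.8 = 96, or 48 per group. This reproduces.
- The BP differences cannot be reproduced without an SD. The unpaired t-test with 48 per group has 90% power at d = 0.669 SD, so the implied SDs are 10/0.669 = 15.0 to 15/0.669 = 22.4 mmHg (SBP) and 5/0.669 = 7.5 to 10/0.669 = 15.0 mmHg (DBP).

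**2. Variance of the week-16 contrast, no range restriction** (in units of SD²).
- Change score: 2(1−r). Baseline-adjusted: 1−r². Ratio adjusted/change: (1+r)/2.
- r=0.5: 0.75, so 25% lower. r=0.7: 0.85, so 15% lower.
- Outside that range: 35% lower at r=0.3 and 10% lower at r=0.8.

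**3. The same contrast under the Protocol's qualifying range.** Let k be the restricted baseline variance divided by the unrestricted one. The change score then has variance (1−r²) + (1−r)²k, and the ratio is (1+r)/[(1+r)+(1−r)k].

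| Outcome, implied SD | k | Reduction, r=0.5 | Reduction, r=0.7 |
|---|---|---|---|
| SBP, 15 | 0.46 | 13% | 8% |
| SBP, 22.4 | 0.24 | 7% | 4% |
| DBP, 7.5 | 0.42 | 12% | 7% |
| DBP, 15 | 0.14 | 4% | 2% |

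Example: SBP, SD 15, r=0.5 gives 1.5/(1.5 + 0.5×0.46) = 0.87. The Inclusion/Exclusion criteria state a looser and/or rule, for which the reduction lies between this table and step 2.

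**4. Power of the 2-df test at d = 0.669 SD** (SD read as raw, unrestricted, complete data). The noncentrality is λ = 24·μ′V⁻¹μ, where 24 = 48/2 and μ holds the week-8 and week-16 effects. V is the covariance of the two changes (planned) or of the two follow-up values given baseline (adjusted). The F tests have 2 and 93 df (planned) or 2 and 92 df (adjusted).

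| r | Effect | λ planned → adjusted | Power planned → adjusted |
|---|---|---|---|
| 0.5 | sustained (d, d) | 14.3 → 21.5 | 93% → 99% |
| 0.5 | half at week 8 (d/2, d) | 10.7 → 14.8 | 83% → 93% |
| 0.7 | sustained | 23.8 → 29.8 | 99.4% → 99.9% |
| 0.7 | half at week 8 | 17.9 → 21.2 | 97% → 99% |

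If the plan's SDs are of change instead, the figures at r=0.7 are 93% → 97% and 83% → 89%.

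**5. Validity.** Simulated type I error (48 per arm, 4,000 runs per setting, r of 0.4, 0.6 and 0.8) was 0.048–0.057 for the change contrast, the 2-df interaction and the baseline-adjusted test alike.

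**6. The imbalance rule.** If a difference means p<0.05 (an assumption), any given variable is adjusted for in about 5% of randomised trials. At least one of the nine enters by chance in up to 1 − 0.95⁹ = 37%. That figure assumes independence, which BMI and body weight clearly breach.

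**The case against.** The best defence is that the plan uses a standard, valid method and mostly meets its own power target.

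- A reader might infer that baseline BP is ignored or that the test is biased. Neither is supported. The hypothesis concerns changes, so baseline is subtracted, and type I error is held.
- A reader might infer that the trial is underpowered. The documents do not show this. At r of 0.5 to 0.7 (SD read as raw, unrestricted) the planned 2-df test has at least 93% power for a sustained effect. It falls below 90% (83%) only for a half effect at week 8 near r=0.5, and even there a baseline-to-week-16 change contrast, of the kind the plan allows, has 90%. That contrast falls short only if r is below 0.5 (78% at r=0.3) with the SDs read as raw.
- A 1-SE chance difference in baseline SBP moves the week-16 change contrast by (1−r)·SD·√(2/48), or 0.9 to 2.3 mmHg unrestricted. It is tempting to count this as a second harm. It averages to zero over randomisation and is the source of the extra variance in step 2.
- A reader might infer that chance selects the primary model. It does not. The imbalance rule governs only the later ANCOVAs. The confounder list is not closed, so a baseline-BP ANCOVA is not ruled out.
- The plan does not say whether the primary BP is ABPM or the seated BP taken at every visit. If it is seated BP, the degrees of freedom and truncation factors above do not apply as computed.

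All of this stands. It limits the size of the point but does not remove it: adjustment is at least as precise in every case computed here, and the plan does not prespecify it.

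**Conclusion.** The point holds as one of efficiency and prespecification. The primary comparison is valid but gives up precision available from data already collected. The gain from adjustment is moderate at best (25% of the variance at r=0.5 without restriction) and may be slight (about 2% at r=0.7 for DBP with the larger implied SD under the qualifying range). The range is wide because r, the type of SD, the BP measure and the pre-restriction distribution are not stated. That baseline is a time point with free group means is itself an inference from the text. The imbalance rule is a lesser weakness, confined to supportive analyses. The change is worth making before unblinding because it is nearly free. Nothing here suggests that the planned test would mislead.

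**What to change.** In the same mixed model, prespecify baseline BP as a covariate with a slope that may differ by visit, or keep baseline as an outcome and constrain both arms to a common baseline mean. Do this for SBP and for DBP. In the supportive ANCOVAs, replace the imbalance rule with a short set of prognostic covariates taken from the plan's own list and fixed in advance.

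The cost is a few sentences in the Statistics section. It needs no new measurements or patients, and adjustment lost no power in any case computed. Naming one between-group contrast as primary, and saying whether the 1-year visit enters the model, would also help but are optional. A single week-16 contrast would give up sensitivity to an effect seen only at week 8.

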The Data Safety and Monitoring plan for this study will include a Data Safety and Monitoring Board (DSMB). The DSMB will consist of [name] endocrinologist and diabetes specialist, [name] an adult cardiologist, and [name] RN, BSN, CDE. All members of the DSMB disclose no conflict of interest related to the proposed trial. The DSMB will have a scheduled meeting twice a year or after an additional 30% of the total anticipated subjects have been enrolled to monitor the study progress and integrity to examine the patient laboratory results, and to assess adverse events (see below) to ensure that patients are not exposed to unnecessary risk during the study.

During screening and baseline evaluation and during the study, serum and urinary calcium levels will be monitored to assess for possible risk of hypercalcemia associated with vitamin D intoxication. Serum calcium >10.5 mg/dl or urinary calcium: creatinine ratio >1.0 at screening or during the course of the study would necessitate that the subject be ineligible for randomization or be withdrawn from the study. This decision will be made by the PI or his designated staff without regard to knowledge of treatment group assignment. In addition, 25(OH) vitamin D levels will be provided to a member of the DSMB to review and alert the PI to any subject who should be withdrawn from the study because of a 25-OHD >200ng/ml during the study (57).

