Our *Data Safety Monitoring Plan* includes thorough documentation of any and all Serious Adverse Events (SAE) and reporting to the Human Research Protection Office (HRPO), the Research Subject Advocate and GCRC Advisory Committee. The participant's side effect log will be reviewed at the time of any event, and all participants that note significant concerns about side effects that cannot be easily and safely addressed will be told to stop the study drug. Reporting of adverse events will be conducted with oversight by the Principal Investigator (PI) and the Research Subject Advocate. Summary reports will be provided to the HRPO and the Research Subject Advocate every six months. In case of a SAE, the research coordinator or PI will report the event to the DSMB and to the HRPO according to the current HRPO guidance document. The PI will determine if the SAE is causally related to the study. Other possibly concerning objective findings that indicate potential for harm will be reviewed with the PI, [name], and lead to stopping the study for that subject if either the PI or any nurse caring for the patient in the GCRC feels the participant could be harmed by continuing the study. Any clear evidence of potential harm will lead to stopping the study for that patient. The HRPO will get a summary of the situation unless the dropout is secondary to participant's personal reasons and unrelated to the study. An interim efficacy analysis will be performed when 60 of the targeted 120 subjects have been enrolled. This analysis will focus on the primary endpoint and will permit us to make one of the following decisions: a) Stop the study early if the data suggest that efficacy has already been achieved. b) Stop the study early for reasons of futility if the data suggest that it is unlikely that efficacy will ever be achieved. c) Continue the study with an increase in the target sample size if the data indicate smaller effect sizes that were initially projected but that an achievable increase in the sample size will yield adequate statistical power. d) Continue the study as planned if effect sizes appear to be approximately as projected. The interim analysis will be conducted in accordance with guidelines set forth by the O'Brien Fleming stopping rule.¹ We emphasize, however, that this will only be a guideline. Any final decision to modify the sample size or to stop the study early will be based on multiple considerations that also include efficacy with respect to important secondary outcomes and the consistency of results across key subgroups. Our study will be conducted with the ideas of justice, beneficence and autonomy having primary importance.

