that is covered by their insurance. The initial goal is to reduce blood pressure to 160/ 110 mm Hg over several days, we will follow these patients closely until this ambulatory BP is achieved. Patients with increased urinary calcium/creatinine ratio >1.0 that are unresponsive to oral fluid therapy, will be evaluated in the CRU to determine whether IV fluid therapy is required. We will follow this patients until they achieve urinary calcium/creatinine ratio <1.0. Patients with asymptomatic hypocalcemia that are unresponsive to increased PO Calcium intake we will supervise calcium intake by clinic visits and follow until plasma calcium levels return to normal. If the patient becomes symptomatic and requires a hospitalization, the patient will be withdrawn from the study. Patients that have completed at least 8 weeks in the study and are withdrawn for medical reasons, will continue to be evaluated every 4 weeks for BP monitoring, plasma calcium levels and urinary calcium and creatinine ratio until completing 16weeks from the initiation of the trial. At 16 weeks AMBP monitoring and FMD and macrophages will be obtained.

Summary reports of all Adverse Events (non-serious AEs and SAEs) will be provided to the DSMB before each scheduled meeting and at least every 4 months. If the PI or the DSMB determine that there are an unacceptable number of AEs and/or SAEs reported, the PI may request that the DSMB review (or the DSMB may independently decide to review) the events by unmasked treatment group. If treatment-emergent AEs or SAEs are occurring at an unacceptable rate, the DSMB may recommend to the PI that the study be halted or that the protocol be modified.

References

3. Killilea T. Long-term consequences of type 2 diabetes mellitus: economic impact on society and managed care. *Am J Manag Care* 8:S441-9, 2002
4. Tight blood pressure control and risk of macrovascular and microvascular complications in type 2 diabetes: UKPDS 38. UK Prospective Diabetes Study Group. *Bmj* 317:703-713, 1998

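### The plan has the study team act on the by-arm interim efficacy result, and nothing sends that result to the existing DSMB or limits who sees it

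*Combined protocol and SAP*

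**What the plan says.** All of this stands in the Data and Safety Monitoring Plan of the combined protocol and SAP, unless another section is named.

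- **The look.** "An interim efficacy analysis will be performed when 60 of the targeted 120 subjects have been enrolled". The next sentence begins "This analysis will focus on the primary endpoint and will permit us to make one of the following decisions".
- **The four options.** (a) "Stop the study early if the data suggest that efficacy has already been achieved". (b) Stop for futility. (c) "Continue the study with an increase in the target sample size if the data indicate smaller effect sizes that were initially projected", provided that a feasible increase would restore power. (d) "Continue the study as planned if effect sizes appear to be approximately as projected".
- **The rule.** O'Brien-Fleming is named, but as guidance. The final decision also weighs secondary outcomes and consistency across subgroups.
- **The DSMB.** It meets "to monitor the study progress and integrity to examine the patient laboratory results, and to assess adverse events". It also confirms the PI's view of SAE causality, and one member reviews 25(OH)D levels. For adverse events, "the DSMB may independently decide to review) the events by unmasked treatment group". If event rates are unacceptable, it may advise the PI to halt or change the study.
- **Staff discretion.** Where objective findings suggest possible harm, a participant may be stopped "if either the PI or any nurse caring for the patient in the GCRC feels the participant could be harmed". The PI's causality judgement after an SAE can also lead to withdrawal. Under Protocol, study physicians may identify candidates in their clinics.

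No section says who prepares the interim comparison, who receives it, or that it is confidential.

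**The concern.** Each option turns on the observed difference between arms, so whoever chooses among them must see it or be told it. As written, that is the group running the trial. If the study then continues, the same people recruit, follow and sometimes withdraw patients while knowing how the comparison stands.

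The risk is operational bias: the kind of patient recruited, or the readiness to withdraw a patient, may shift after the look, and nothing in the data would show clearly why. The reader of the final result could not rule this out. An enlarged target has a similar effect, because a sample size chosen from the observed effect lets people work back to that effect.

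**Working it through.** This is a question of governance, so no single figure decides it. The text is compared first. A calculation then shows how likely it is that the trial would continue with the estimate known.

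**1. Who decides?** In the same section the first person is used for minimising patients' risks and for following patients with high blood pressure, which are the study team's tasks. The DSMB always appears in the third person.

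**2. Could the choice be made without by-arm results?** No. Options (a), (c) and (d) are worded in terms of efficacy or effect size, and (b) in terms of the prospect of efficacy. Because the boundary is only guidance and other outcomes and subgroups count, no mechanical rule could be applied on the team's behalf.

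**3. Does another section send the result to the DSMB?** No. Its stated remit is progress, integrity, laboratory results and adverse events. Its power to advise halting is tied to adverse event rates. Unmasked review is given to it for safety but not for efficacy.

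**4. What is still open at the look?** 120 − 60 = 60 patients, or half. This is an upper limit: the trigger is enrolment, while the last on-treatment measurement is at 16 weeks, so more may have been enrolled by the time outcomes are available.

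**5. How likely is continuation with a known estimate?** Inputs from Statistics: 120 recruited, 20% dropout, 90% power, two-sided 0.05, unpaired t-test, detectable SBP difference 10 to 15 mm Hg. The SDs are not given.

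- Plan's own figure: 120 × 0.80 / 2 = 48 per group. It reproduces.
- Detectable difference at 48 per group and 90% power: 0.669 SD (t-test). Implied SBP SD: 10 / 0.669 = 15.0 to 15 / 0.669 = 22.4 mm Hg.
- *Assumption A: all 60 have outcomes, less 20% dropout.* 60 × 0.80 / 2 = 24 per arm, and the information fraction is 24 / 48 = 0.5. The two-look O'Brien-Fleming boundary is |z| = 2.797 (p = 0.0052), with 1.977 (p = 0.048) at the end. The SE is √(2/24) = 0.289 SD, or 4.3 to 6.5 mm Hg. The boundary is 2.797 × 0.289 = 0.81 SD, or about 12 to 18 mm Hg.
- If the true difference equals the detectable one, the expected z is 0.6685 / 0.2887 = 2.316. The chance of crossing is 1 − Φ(2.797 − 2.316) = 0.315, or about 32%. In the other 68% or so the trial goes on, unless futility or other considerations stop it.
- *Assumption B: only half of those have outcomes.* 12 per arm, information 0.25, boundary |z| = 3.92, SE √(2/12) = 0.408 SD. The chance of crossing is 1 − Φ(3.92 − 0.6685/0.408) = 0.011, or about 1%.

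So, at the detectable difference, the boundary would be missed about 68% to 99% of the time. This shows how often the situation could arise. It does not measure bias.

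**The case against.** The strongest reply is that the plan leaves access unspecified and shows no bias. Much of this stands.

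- **A reader might infer that nurses, coordinators and recruiters will know the effect.** The text does not say so, nor does it literally say that the PI receives the estimate. What follows is narrower: those who decide would need it, and nothing keeps it from others.
- **A reader might infer that the look breaks the blind.** It does not. Placebo is matching and dispensed by the pharmacy, and an aggregate effect does not reveal one patient's arm. Withdrawing more patients from one arm would require guessing assignment, for instance from blood pressure response. That is possible, but the documents do not show it.
- **A reader might infer that withdrawals are unguarded.** Calcium-based withdrawals and SAE causality are to be judged without reference to arm, and the DSMB confirms causality. The high-BP step has a numeric threshold with ABPM confirmation, and antihypertensive treatment follows the primary care doctor's advice where there is one. The evaluators' names are removed, so it cannot be verified that they belong to the deciding team.
- **A reader might try to put a mm Hg value on the bias.** The inputs are not in the documents. Withdrawn patients also do not simply leave the comparison: Statistics specifies intention-to-treat with a mixed model, and patients withdrawn for medical reasons after at least 8 weeks are followed to 16 weeks with ABPM. Earlier withdrawals are less protected.
- **A reader might take the first person to include the DSMB**, since the sentence sits in the monitoring plan. No other sentence supports that.

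The non-binding boundary also bears on type I error, which is a separate question. It matters here only because it makes sight of the data necessary.

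**Conclusion.** The concern holds as a weakness in who handles the interim result. Followed as written, the plan puts by-arm efficacy before the people who run the trial, with up to 60 of 120 patients still to be enrolled, while the DSMB that already handles unmasked safety data has no stated part. This is more than a missing detail, because the plan names a decision-maker and the change would replace it.

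Bias is neither demonstrated nor computable from the documents. Masked assignment, confirmation of causality by the DSMB, the intention-to-treat analysis and follow-up after week 8 all limit it. The conclusion rests on two readings: that the first person means the study team, and that the four options cannot be chosen without by-arm results. The change should be made, but the gap does not by itself invalidate the trial.

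**What to change.** Amend the interim-analysis and DSMB paragraphs of the Data and Safety Monitoring Plan as follows.

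1. An analyst without patient contact prepares the by-arm interim report. A study statistician unblinded for this purpose could serve.
2. Only the DSMB sees the report, in closed session, and interim efficacy is added to its remit.
3. The DSMB returns only a recommendation: stop, continue, or a revised target.
4. Any sample-size rule is written beforehand and held by the DSMB. The target is revised in coarse steps, so that the effect cannot readily be back-calculated from it.
5. Investigators and staff in patient contact see no by-arm efficacy results until database lock.

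**Cost.** An unblinded analyst must be named, because the listed DSMB is two physicians and a nurse. Written rules for futility and sample size must be drafted, since none exist now. The board already meets twice a year or after each further 30% of enrolment (0.30 × 120 = 36, then 72), so a look at 60 may need its own session. The investigators lose sight of interim results.

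### The O'Brien-Fleming efficacy boundary is declared non-binding and no limits are printed, so an efficacy stop below it is allowed and the planned two-sided 5% error is not guaranteed

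*Combined protocol and SAP*

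**What the plan says.** All references are to the combined protocol and SAP. The Data and Safety Monitoring Plan sets one interim efficacy analysis when 60 of the 120 subjects have been enrolled. It states: "This analysis will focus on the primary endpoint". Four outcomes are listed: an efficacy stop, a futility stop, a larger sample size, or continuing as planned. The efficacy option reads: "Stop the study early if the data suggest that efficacy has already been achieved". The rule is named: "The interim analysis will be conducted in accordance with guidelines set forth by the O'Brien Fleming stopping rule". Its status follows at once: "We emphasize, however, that this will only be a guideline". The plan then says: "Any final decision to modify the sample size or to stop the study early will be based on multiple considerations", and describes these as considerations "that also include efficacy with respect to important secondary outcomes and the consistency of results across key subgroups".

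The Statistics section sets a two-tailed type I error of 0.05 for the calculation of detectable differences with 48 completers per group. It names SBP and DBP as primary and analyses them with a repeated-measures mixed model, for which no significance level is given. It does not mention the interim look. No interim critical value, spending function or final significance level appears anywhere.

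**The concern.** A group sequential boundary protects the type I error only if an efficacy claim at the interim requires crossing it. Departures in the other direction are harmless: continuing after the boundary is crossed, or treating a futility rule as advisory, does not raise the error. The one departure that does raise it is stopping for efficacy when the boundary has not been crossed.

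The wording here leaves that departure open. The rule is advisory, the efficacy option asks only that the data suggest efficacy, and secondary outcomes and subgroups may weigh on the decision in either direction. If the trial stopped this way, or reported a positive final result after the option had been open, the error rate behind the result could not be stated. It might exceed the 5% used for planning.

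**Working it through.** **Inputs from the document.** Two-sided alpha 0.05, power 90%, 120 recruited, 20% dropout (Statistics); one look at 60 enrolled (Data and Safety Monitoring Plan); outcome testing at baseline, 8 and 16 weeks (Protocol). The planned size reproduces: 120 × 0.8 / 2 = 48 per group.

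**Assumptions.** The trigger counts enrolled patients, not patients with 16-week data, so the information fraction t is probably below one half. I use t = 0.50 and t = 0.35. The interim thresholds in the override cases are also assumed, because the plan gives none. All figures are per endpoint and use a normal approximation.

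**Method.** Under the null, the interim and final statistics have correlation √t. With the trial continuing when −l < Z1 < u, and final critical value c:

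total error = P(Z1 ≥ u) + P(Z1 ≤ −l) + ∫ from −l to u of φ(z) · [1 − Φ((c − √t·z)/√(1−t)) + Φ((−c − √t·z)/√(1−t))] dz.

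**Rule kept.** The classic two-look rule sets the interim limit at c/√t. At t = 0.50 the solution is c = 1.9774, so the limits are 1.9774/0.7071 = 2.797 (p = 0.0052) and 1.977 (p = 0.048), and the total is 5.00%. Using these same limits at t = 0.35 gives 5.09%. Keeping 2.797 at the interim but testing at 0.05 at the end gives 5.20% (t = 0.50) and 5.29% (t = 0.35).

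**Favourable-direction override.** Here u is lowered to the assumed threshold and l stays at 2.797, since a discretionary efficacy stop would be used only when vitamin D looks better. Each cell gives t = 0.50 / t = 0.35.

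| Interim efficacy stop at | Final level 0.05 | Final level 0.048 |
|---|---|---|
| p<0.01 | 5.33 / 5.45% | 5.13 / 5.26% |
| p<0.025 | 5.81 / 6.02% | 5.63 / 5.83% |
| p<0.05 | 6.75 / 7.04% | 6.58 / 6.86% |

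**Both directions.** If sub-boundary stops in either direction are counted, the p<0.05 case gives 8.31 / 8.78% (final 0.05) or 8.15 / 8.62% (final 0.048). By symmetry, the favourable-direction error in that case is half of this, about 4.1-4.4% against a nominal 2.5%. That one-sided error is essentially the same whether or not unfavourable overrides are counted.

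**Occasional override.** Suppose only a share s of favourable interim results between p = 0.0052 and p = 0.05 led to a stop, with final level 0.048. The total is then the kept-rule figure plus s times the increase from full override:

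- t = 0.50: 5.00 + 0.10 × (6.58 − 5.00) = 5.16%; with s = 0.25, 5.39%.
- t = 0.35: 5.09 + 0.10 × (6.86 − 5.09) = 5.27%; with s = 0.25, 5.53%.

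**Limits after the fix.** An O'Brien-Fleming-type spending function with 0.025 per side, α(t) = 2 − 2Φ(z₀.₀₁₂₅/√t), gives 2.963 / 1.969 at t = 0.50 and 3.613 / 1.961 at t = 0.35. Each pair totals 5.00%.

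**The case against.** The best defence is that the text has a more natural reading. The interim is to follow the named rule, and the other considerations are introduced as additions to it. Checks on secondary outcomes and subgroup consistency usually restrain a stop, and restraint does not raise the error. Monitoring boundaries are also commonly called guidelines. This stands to the extent that the plan cannot be said to intend a stop below the boundary. It does not remove the gap, because no sentence limits the considerations to restraint and the advisory status is given special emphasis.

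A second defence is that the limits can be derived: alpha 0.05, one look at 60 of 120 and the named rule suggest 2.797 and 1.977. That holds only for the classic version at exactly half the information. The spending version gives different values even at one half, and the trigger does not ensure one half. A derived limit would in any case still be advisory. The trigger itself matters little: limits for exactly half information used at t = 0.35 cost about 0.1 point.

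Third, the futility stop would offset some inflation. It has no stated limit and falls under the same advisory wording, so it cannot be relied on for control.

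A reader might infer more from option (c), the sample size increase: "Continue the study with an increase in the target sample size if the data indicate smaller effect sizes that were initially projected". Figures of 5.5-7.0% can be obtained if the sample size goes to a cap even when adequate power is out of reach. The text does not authorise that. It requires "but that an achievable increase in the sample size will yield adequate statistical power". On that reading, with assumed caps of 1.5 to 4 times the planned size and an unadjusted final test at 0.048 or 0.05, the error is about 4.7-5.2%. As worded, the option adds little.

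**Conclusion.** The concern holds and should be fixed. The plan permits an efficacy stop below its named boundary through a stated rule, not merely through missing detail, and it prints no limit or final level. The planned two-sided 5% is therefore not guaranteed.

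The size is modest unless the rule is set aside at a conventional p-value. It is 5.2-5.3% if only the final level is left at 0.05, 5.2-5.5% under occasional override, and about 5.1-7.0% across the favourable-direction overrides. These figures rest on assumed thresholds, override shares and information fractions, because the document supplies none. The conclusion about the wording is firm; the size is illustrative.

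A reader might infer that the trial runs at an error rate above 8%. The documents do not support that. The 8.2-8.8% range is an extreme that needs stops at p<0.05 and counts unfavourable sub-boundary stops as well, whereas the option concerns efficacy achieved. Having two primary endpoints, SBP and DBP, raises a separate multiplicity question that exists without an interim look and is not counted here.

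**What to change.** 1. Make the efficacy boundary binding: the trial may stop for efficacy only if it is crossed. Secondary outcomes and subgroup consistency may withhold an efficacy stop but may not justify one below the boundary. Futility may stay non-binding.

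2. State the interim limit and the final level. Preferably use an O'Brien-Fleming-type spending function at the actual information fraction (2.96 / 1.97 at 0.50; 3.61 / 1.96 at 0.35), which also deals with the enrolment-based trigger. Alternatively, fix the look at exactly half the information and use 2.797 / 1.977 (p<0.0052, then p<0.048). Say whether the limits apply to SBP, DBP or both.

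3. As a precaution only, if the sample size is raised because of the observed interim effect, use a combination test with the originally planned weights.

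The cost is protocol wording and the discretion to stop for efficacy below the boundary. At half information, power at the planned detectable difference falls from 90.0% to 89.8% (classic) or 89.9% (spending). From the final critical value alone, the detectable difference grows by at most a factor (1.977 + 1.282)/(1.960 + 1.282), about 1.005. The unrounded increase of 0.54% on the upper SBP figure of 15 mm Hg is 0.08 mm Hg.
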